Study Design

NCT numer: *pending*

Title: Assessment of Vascular Complications in Patients Undergoing Peripheral Revascularization: The Impact of SGLT-2 Inhibitors

Type: Retrospective, observational study

1. **Study Objective:** To assess the impact of SGLT2 inhibitors on vascular complications in patients undergoing peripheral revascularization.

Specific Objective: To evaluate the occurrence of 3-point MACE (Major Adverse Cardiac Events) or MALE (Major Adverse Limb Events) after vascular surgery procedures (both open and minimally invasive), performed electively or urgently, in patients previously treated with SGLT2 inhibitors.

Follow-up period: ONE YEAR: assessment at 30 days, 3 months, and 12 months post-procedure.

Definition of MACE:

Myocardial infarction (MI) not resulting in death

Stroke affecting the central nervous system (CNS) not resulting in death

Cardiovascular death

**Definition of MALE:*

Untreated loss or deterioration of patency in a previously revascularized vessel (decline in ABPI)

Repeat intervention in the revascularized segment due to loss of patency

Amputation (above or below the knee) of the revascularized limb

2. **Primary Outcome Measures:** MALE and MACE

3. **Secondary Outcome Measures:** Individual components of MALE and MACE

4. **Additional Secondary Outcome Measures:**

Surgical complications such as surgical site infection (SSI) or major bleeding

Acute kidney injury

Need for reintervention (readmission and procedure in the same segment)

Foot necrosis

“Minor amputation” (defined as amputation within the foot)

Hospitalization due to heart failure

5. Inclusion and Exclusion Criteria

Inclusion Criteria:

Surgical procedure on peripheral vessels due to acute or chronic ischemia

Use of SGLT2 inhibitors (reason for initiation is irrelevant: CKD – chronic kidney disease / cardiovascular indications / diabetes) - Condition required only for the drug-exposed group.

Ability to follow up the patient for at least 30 days up to 1 year after the vascular procedure

Exclusion Criteria:

Vascular injury as the reason for the procedure

Amputation for reasons other than ischemia (e.g., tumor, neuropathy, trauma without concomitant ischemia)

Planned revascularization procedure not involving lower limbs (e.g., coronary or carotid vessels)

Planned amputation due to ischemia, partial, in the area of the operated limb

Planned other major surgical procedure with high cardiovascular risk

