6. Collected Parameters (at admission to the vascular surgery ward):

Laboratory tests:

Complete blood count

Blood creatinine with eGFR

Urinalysis

Full lipid panel

HbA1c (if patient has diabetes)

Fasting glucose (FG)

Anthropometric data: weight, height – calculation of BMI (body mass index)

Demographics: age and biological sex

Medical history (structured questions):

a. Does the patient have diabetes? (If YES: record type 1 or 2; duration in years or <1 year if less than one year; medications for diabetes; presence of chronic microvascular complications: neuropathy, albuminuria, diabetic eye disease)

b. Does the patient have a history of:

Myocardial infarction (MI)

Stroke

Diagnosed peripheral arterial occlusive disease (PAD) (if YES: date of diagnosis; date of symptom progression that led to current procedure)

Previous interventions on coronary vessels (if YES: date in years, e.g., 5 years ago, or <1 year if within the past year)

Previous interventions on carotid or other head/neck vessels (if YES: date in years, e.g., 5 years ago, or <1 year if within the past year)

Additional Collected Parameters :

Previous interventions on lower limb vessels (including iliac arteries – e.g., external iliac artery): indicate the date in years, e.g., 5 years ago, or <1 year if within the past year

History of aortic aneurysm surgery (thoracic or abdominal); if YES, indicate date

History of heart failure treatment

Hypertension

Hyperlipidemia

History of cardiac arrhythmias (e.g., atrial fibrillation – AF)

Thyroid disease (hypothyroidism/hyperthyroidism only); if YES, provide most recent TSH value, if known or measured in hospital

Smoking status:

Current smoker?

If NO, date of cessation in years, <1 year if within the past year

Includes e-cigarettes (if yes, mark YES)

Chronic medications before hospital admission (excluding supplements) – chemical names

Recent interruptions in chronic medications

SGLT2 inhibitor (flozin) used before procedure: type, dose, duration, indication (diabetes, cardiology, nephrology)

7. Parameters to collect during follow-up (post-procedure):

Medications prescribed for chronic use: chemical names

Whether prescribed medications were taken regularly during follow-up

Occurrence of any of the following events**:

- a. Myocardial infarction not resulting in death
- b. Stroke (central nervous system) not resulting in death
- c. Cardiovascular death

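### Chronic kidney disease is a named reason for the drug and acute kidney injury is an outcome, yet no CKD, dialysis or transplant history is collected in either group and albuminuria is asked only of diabetics

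*Protocol*

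**What the plan says.** Section 5 of the Protocol makes SGLT2 inhibitor use an inclusion criterion whatever the indication: "reason for initiation is irrelevant: CKD – chronic kidney disease / cardiovascular indications / diabetes". It adds "Condition required only for the drug-exposed group", which implies a comparison group of non-users. The same section admits both acute and chronic ischemia, and the specific objective in section 1 covers elective and urgent procedures.

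Section 6 lists what is recorded at admission. The kidney-related items are:

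- Laboratory tests, all patients: "Blood creatinine with eGFR" and a urinalysis.
- Medical history item a, which opens with "Does the patient have diabetes? (If YES: record type 1 or 2". Within that YES branch it asks for "presence of chronic microvascular complications: neuropathy, albuminuria, diabetic eye disease".
- For users of the drug: "SGLT2 inhibitor (flozin) used before procedure: type, dose, duration, indication (diabetes, cardiology, nephrology".

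The other history items cover MI, stroke, PAD, earlier arterial interventions, aneurysm surgery, heart failure, hypertension, hyperlipidemia, arrhythmia and thyroid disease. CKD is not among them, and neither dialysis nor transplantation is mentioned anywhere in the document. Acute kidney injury is an outcome in section 4 and a follow-up event in section 7 (item i).

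**The concern.** Kidney disease is a reason for exposure by the protocol's own account, and it is plausibly related to MACE, MALE and acute kidney injury. That makes it a candidate for confounding by indication. Of the three named indications, diabetes and cardiovascular disease have history items for every patient; kidney disease has none.

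Two things are at stake. First, adjustment for kidney disease would rest on one admission eGFR and a urinalysis, with no information on chronicity or dialysis and, in non-diabetics, no albuminuria item. Second, a patient already on chronic dialysis cannot meaningfully be counted as at risk of acute kidney injury, and no field would let the analyst find such patients. A statistical analysis plan can choose covariates and define analysis sets, but it cannot recover history that was never abstracted.

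**Working it through.** The protocol states no sample size, event rate or dialysis prevalence, so it has no figure to reproduce. The main check is a reading of the data-collection list by type of patient.

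**Step 1. Kidney information available (sections 5 and 6)**

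| Patient | Admission eGFR and urinalysis | Albuminuria item | Recorded chronic kidney diagnosis |
|---|---|---|---|
| User, nephrology indication | yes | only if diabetic | yes, through the indication |
| User, diabetes or cardiology indication | yes | only if diabetic | no |
| Non-user, diabetic | yes | yes | no |
| Non-user, not diabetic | yes | no | no |

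The albuminuria item depends on diabetes, not on drug use. The difference between groups in recorded diagnosis is confined to the first row. Missing CKD, dialysis and transplant history is common to all four rows.

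**Step 2. What the common measures can and cannot do**

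Creatinine is taken at a single time, on admission. In a stable elective patient it is a reasonable baseline. In acute ischemia one value cannot show whether a low eGFR is long-standing or new. A very low eGFR raises suspicion of dialysis but does not distinguish it from advanced CKD without dialysis or from acute injury. The medication list by chemical name is at most an indirect sign.

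**Step 3. Illustration of size (all inputs assumed; none is in the protocol)**

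- Chronic dialysis in a share d of non-users, with d = 3%, 5% or 10%, and in about 0% of users.
- Twelve-month risk of MALE or cardiovascular death: 35% on dialysis, 15% otherwise.
- Acute kidney injury: 12% off dialysis, 0 on dialysis.
- No drug effect and no covariate adjustment.

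MALE or cardiovascular death: RR = 0.15 / [0.35d + 0.15(1 - d)].

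- d = 0.03: 0.15 / (0.0105 + 0.1455) = 0.15 / 0.156 = 0.96
- d = 0.05: 0.15 / (0.0175 + 0.1425) = 0.15 / 0.160 = 0.94
- d = 0.10: 0.15 / (0.0350 + 0.1350) = 0.15 / 0.170 = 0.88

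Acute kidney injury: RR = 0.12 / [0.12(1 - d)] = 1 / (1 - d).

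- d = 0.03: 1 / 0.97 = 1.03
- d = 0.05: 1 / 0.95 = 1.05
- d = 0.10: 1 / 0.90 = 1.11

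If the kidney-injury comparison is limited to patients not on dialysis, it becomes 0.12 / 0.12 = 1.00, the true value under these assumptions.

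**The case against.** The strongest reply is that a kidney covariate already exists. Creatinine with eGFR and a urinalysis are collected identically in users and non-users, and the choice of adjustment variables and of the denominator for acute kidney injury properly belongs to a statistical analysis plan that is not shown. Most of this stands. The gap is in chronicity, dialysis and transplant status, and albuminuria in non-diabetics; it is not an absence of kidney data. Nor is the missing denominator rule a fault in itself. The fault is that no field would allow the rule to be applied.

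A reader might infer something stronger: that kidney disease is documented in users through the indication and in non-users only through admission tests, so that adjustment is bound to be uneven. The protocol does not support that. Diabetic non-users also get the albuminuria item. A user treated for diabetes or a cardiac reason who also has CKD is documented just like a non-user. Nothing says that the indication field will serve as a kidney covariate, and a field that exists only in the exposed could not do so across groups.

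The risk ratios are also open to challenge, fairly. Every input is assumed. MALE or cardiovascular death together is not an outcome that the protocol defines; its primary outcomes are MALE and MACE. The calculation models an imbalance in dialysis, which is unrecorded in both groups alike. Finally, the figures are crude, and adjustment for eGFR would reduce the one for limb events and death.

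**Conclusion.** The point holds as a gap in data collection common to both groups. CKD is a named reason for treatment and acute kidney injury is an outcome, but chronic kidney disease, dialysis and transplant are recorded for no one as history, albuminuria is not asked of non-diabetics, and only users with a nephrology indication carry a recorded chronic kidney diagnosis. Admission eGFR covers part of this. It covers least in acute presentations, whose share the protocol does not give, and in patients on chronic dialysis.

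The size cannot be fixed from the document. On the assumed inputs the crude distortion is modest, in favour of the drug on MALE or cardiovascular death and against it on acute kidney injury. These figures illustrate direction and order of magnitude; they do not estimate the bias that would remain after adjustment. Recruiting more patients would not remove it. The gap is not fatal to the study, but it is cheap to close and should be closed while charts are being abstracted.

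**What to change.** In section 6, for every patient whether or not diabetic and whether or not a user of the drug, add:

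1. CKD diagnosed before admission (yes/no/NZ, with stage).
2. Chronic dialysis or kidney transplant (yes/no/NZ, recorded so that the two can be told apart).
3. Albuminuria, moved out of the diabetes branch.
4. Last creatinine before the index admission, with its date.

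Use these in the same way in both groups, alongside admission eGFR, and do not use the drug indication as a stand-in for CKD. Count acute kidney injury only among patients not on chronic dialysis.

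The cost is slightly more abstraction: four items from the same charts, and more work if charts already closed must be reopened. Earlier creatinine and albuminuria will be unavailable in some patients. The NZ code in the Notes / Guidelines already provides for that, and the proportion coded NZ should be reported by group.

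### Prior MI and prior stroke are recorded without dates, so how recent they were is only partly captured for the MACE comparison

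*Protocol*

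**What the plan says.** The protocol describes itself as "Type: Retrospective, observational study" and compares patients taking an SGLT2 inhibitor with patients who are not. Section 2 makes MACE a primary outcome alongside MALE. The MACE definition in section 1 consists of non-fatal MI, "Stroke affecting the central nervous system (CNS) not resulting in death" and cardiovascular death. The follow-up line reads "Follow-up period: ONE YEAR: assessment at 30 days, 3 months, and 12 months post-procedure".

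Medical history item b in section 6 opens with "Does the patient have a history of" and lists MI, stroke, PAD, coronary interventions and carotid or other head/neck interventions. MI and stroke stand alone, with no date request. The others are dated, for example "Previous interventions on coronary vessels (if YES: date in years, e.g., 5 years ago, or <1 year if within the past year". Under the additional parameters of section 6, lower-limb interventions and aortic aneurysm surgery are dated too. Heart failure treatment, hypertension, hyperlipidemia and arrhythmia are not.

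On exposure, the inclusion criteria in section 5 state "reason for initiation is irrelevant: CKD – chronic kidney disease / cardiovascular indications / diabetes". Section 6 also records type, dose, duration and indication of the flozin for those who take one. The notes at the end of the protocol add no date for prior MI or stroke.

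**The concern.** Without randomisation, the comparability of users and non-users depends on the covariates collected. An MI or stroke shortly before the procedure plausibly carries a higher 12-month risk of another event than one from decades ago, yet both receive the same code. Because cardiovascular disease is one accepted reason for starting the drug, a recent cardiac event could itself lead to the prescription. Groups that look balanced on the yes/no field could then differ in recency, and matching or adjusting on that field would not remove the difference. At stake are the MACE contrast and its MI and stroke components, which are secondary outcomes under section 3. An analysis plan can choose how to adjust, but not for a variable that was never abstracted.

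**Working it through.** The protocol states no event rate, sample size or adjusted estimate, so there is no figure of its own to reproduce. The check has two parts.

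**1. Which history items in section 6 are dated**

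| Item | Date requested |
|---|---|
| MI | no |
| Stroke | no |
| PAD | yes (diagnosis and symptom progression) |
| Coronary interventions | yes |
| Carotid or other head/neck interventions | yes |
| Lower-limb interventions | yes |
| Aortic aneurysm surgery | yes |
| Heart failure treatment, hypertension, hyperlipidemia, arrhythmia | no |

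Within item b, 3 of 5 items are dated, and the 2 undated ones are MI and stroke. Setting those two aside, all 5 vascular disease or intervention items are dated. If the four other cardiovascular conditions are counted as well, the figure is 5 of 9.

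**2. Whether another listed field supplies recency**

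- A coronary intervention date can date an MI only if that MI was treated by intervention.
- A carotid intervention date does not date a stroke.
- Flozin duration and indication exist only for users, have no counterpart in the comparison group, and do not date an event.

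Recency is therefore partly captured, not absent.

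**3. Illustration of size.** Every input here is an assumption; none comes from the protocol. There is no drug effect; 35% of each group has a prior MI or stroke; 12-month MACE risk is 25% if the event was under 1 year ago, 12% if older, and 7% with no such history. Let p be the share of prior events that are recent.

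Risk in the history stratum = 0.25p + 0.12(1 − p)

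Risk standardised over yes/no history = 0.35 × (history-stratum risk) + 0.65 × 0.07

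With p = 0.40 in users and 0.20 in controls:

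- Users, history stratum: 0.40 × 0.25 + 0.60 × 0.12 = 0.172
- Controls, history stratum: 0.20 × 0.25 + 0.80 × 0.12 = 0.146
- Ratio in the history stratum: 0.172 / 0.146 = 1.18
- Standardised, users: 0.35 × 0.172 + 0.65 × 0.07 = 0.1057
- Standardised, controls: 0.35 × 0.146 + 0.65 × 0.07 = 0.0966
- Risk ratio adjusted for yes/no history: 0.1057 / 0.0966 = 1.09

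| Recent share, users vs controls | Adjusted risk ratio (true value 1.00) |
|---|---|
| 30% vs 20% | 1.05 |
| 40% vs 20% | 1.09 |
| 50% vs 15% | 1.17 |
| 20% vs 40% | 0.91 |
| equal | 1.00 |

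These ratios adjust for yes/no history alone. They give no credit for the coronary and carotid intervention dates.

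**The case against.** A yes/no history of MI and stroke is a coherent baseline variable, and the protocol contradicts nothing by using it. The dated items are mostly interventions, plus PAD, the disease under study; the undated ones are diagnoses. The omission may therefore be deliberate. The adjustment model belongs to an analysis plan that is not at hand, and the Excel sheet named in the notes is not shown, so its exact columns are unknown. The effect concerns MACE only, and every number in the illustration is assumed.

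Much of this stands. It limits the weight of the point but does not remove it: section 6 is the protocol's own list of what to collect, and it requests no date for these two items.

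A reader might go further and infer that MACE cannot be adjusted for recency at all, or that the information is lost. The protocol does not support either. Dated coronary and carotid interventions are partial proxies in both groups. Flozin indication and duration allow some check, among users, of whether recent cardiac disease prompted the prescription. Because the study is retrospective, the dates can probably still be found in the charts, though going back for them later costs more than requesting them during abstraction.

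**Conclusion.** The point holds as a gap in covariate collection. The recency of two histories that match MACE components is only partly captured, and adjustment on yes/no may leave residual confounding in the MACE comparison. MALE, the other primary outcome, is not directly affected.

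Neither size nor direction can be derived from the protocol. The illustrative range of 0.91 to 1.17 depends wholly on the assumed prevalence, risks and recency splits; the splits that double the users' recent share or raise it by half give 1.09 and 1.05. A reader might take these ratios as evidence that the study is biased, or biased against the drug. They show neither: the sign reverses with the split, and balanced recency gives no bias.

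**What to change.** In section 6, item b, add to both MI and stroke the date format the form already uses for interventions: years since the event, or under 1 year. For events under 1 year, also record months before the index procedure, because the existing format alone cannot separate a few weeks from 11 months. Enter NZ where the date is unknown, as the notes already provide. When adjusting or matching the MACE comparison, use recency (none, 1 year or more, under 1 year) in place of yes/no for each history.

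The cost is two further fields in the abstraction sheet, usually read from the chart entry that gives the yes/no answer. Abstraction takes slightly longer, and some old events will have no date, so the analysis will need a stated way to handle patients with a known event of unknown date.

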- d. Deterioration of previously revascularized vessel (ABI decrease) confirmed by visit to vascular surgeon/angiologist
- e. Repeat intervention in previously revascularized segment due to deterioration
- f. Amputation (above or below knee) of revascularized limb
- g. Deep surgical site infection (other than skin)
- h. Major bleeding: at surgical site, gastrointestinal, other (specify location)
- i. Acute kidney injury
- j. Necrosis of the foot
- k. "Minor amputation" (foot or toes)
- l. Hospitalization due to heart failure

8. SGLT2 inhibitor (flozin) continuation during follow-up (up to 1 year):

Did the patient continue taking the flozin as before the procedure?

If not, was it discontinued immediately before surgery or during follow-up? Indicate timing.

9. Hypoglycemia in patients with diabetes:

Were there any hypoglycemic events? (Symptoms confirmed by blood glucose <70 mg/dL or asymptomatic blood glucose <70 mg/dL)

10. Type of procedure performed:

Record the specific vascular intervention.

11. ABI measurements:

Pre-procedure ABI

Post-procedure ABI

ABI if the patient underwent another procedure during follow-up due to restenosis

Notes / Guidelines:

SGLT2 inhibitors (flosins) – include also combination drugs (e.g., Xigduo). If the patient takes a combination drug, mark each component in the Excel sheet (e.g., Lonamo Duo → mark both metformin and DPP-4i; Dipeptidyl Peptidase-4 inhibitors).

If information is unavailable, enter “NZ” to confirm it was checked.

For stroke, include TIA (Transient Ischemic Attack) if confirmed.

*MALE definition, comments: Untreated loss or deterioration of patency in a previously revascularized vessel, measured by: ABI decrease (objective), Restenosis on ultrasound (objective), Shortening of claudication distance (subjective/clinical). Comment: If ABI is not performed at a center, other listed criteria may be used to confirm MALE. ABI is not strictly required if another criterion is met.

**For follow-up events (point 7):

Myocardial infarction not resulting in death, CNS stroke not resulting in death, cardiovascular death, or deterioration of previously revascularized vessel. Comment: “Deterioration requiring

visit and confirmed by physician" is sufficient; ABI measurement is optional but preferred for objective confirmation. Record method of confirmation.

For ABI (point 11): If ABI was not measured at any of the time points, mark "not performed."

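### The listed baseline fields capture limb severity and urgency only through partial proxies, so the limb contrasts between SGLT2 inhibitor users and non-users could be only partly adjusted if nothing else is abstracted

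*Protocol*

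**What the plan says.** The specific objective (Section 1) covers procedures "performed electively or urgently, in patients previously treated with SGLT2 inhibitors". The inclusion criteria (Section 5) accept a "Surgical procedure on peripheral vessels due to acute or chronic ischemia", and attach to SGLT2 inhibitor use the remark "Condition required only for the drug-exposed group". An unexposed comparison group is therefore implied in a study described as retrospective and observational.

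On the limb, Section 6 asks for "Diagnosed peripheral arterial occlusive disease (PAD) (if YES: date of diagnosis; date of symptom progression that led to current procedure" and for "Previous interventions on lower limb vessels", dated in years. Section 10 asks for the specific intervention. Section 11 asks for pre-procedure ABI, and the notes allow ABI to be marked as not performed.

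Section 5 excludes "Planned amputation due to ischemia, partial, in the area of the operated limb". Section 7 asks, after the procedure, for "Occurrence of any of the following events", and item j of that list is "Necrosis of the foot". MALE, which includes above- or below-knee amputation, is a primary outcome. Foot necrosis is an additional secondary outcome.

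**The concern.** The protocol itself names two ways in which its patients differ, elective versus urgent and acute versus chronic, and then lists no baseline field for either. Nor does it list a clinical stage of ischemia or tissue loss at admission. In a non-randomized comparison these are natural candidates for confounding of limb outcomes. If users and non-users differ on them, the MALE and amputation contrasts carry that difference, and an analysis can remove only the part that the recorded proxies explain.

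This is not a matter merely left to the SAP. An SAP chooses how to adjust, but it can use only what has been abstracted, and the list of fields is what this protocol sets out to fix.

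A lesser, separate point concerns ascertainment. Foot necrosis is recorded after the procedure with no admission counterpart, so the listed fields cannot tell new necrosis from necrosis that was already present or has extended.

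**Working it through.** **Field check.** The protocol states no sample size, event rate or effect size, so there is no figure of its own to reproduce. The first check sets the range of patients admitted, and the outcomes used, against every field in Sections 6 to 11.

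| Characteristic | Where it enters | Direct baseline field listed | Indirect information listed |
|---|---|---|---|
| Elective or urgent | Section 1, specific objective | None | Procedure type |
| Acute or chronic ischemia | Section 5, inclusion | None | Procedure type; symptom-progression date, only if PAD was diagnosed |
| Ischemia stage | Not restricted | None | Pre-procedure ABI (may be absent); prior limb interventions; PAD diagnosis date |
| Ulcer or necrosis at admission | Section 4 outcome; Section 7 item j | None | None specific; exclusion of planned partial amputation removes some patients |

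Sections 8 and 9 (continuation of the drug, hypoglycemia) add nothing on the limb. A patient with acute ischemia and no PAD diagnosis would have no symptom-progression date.

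**Illustration of what a proxy leaves behind.** Every input here is assumed; none comes from the protocol.
- The drug has no effect.
- Severe ischemia multiplies MALE risk by R = 2 or 3.
- The share with severe ischemia is pE in users and pC in non-users.
- Groups are of equal size.
- One binary proxy is adjusted for, with sensitivity and specificity both s, the same in both groups.

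Crude RR = [1 + pE(R − 1)] / [1 + pC(R − 1)].

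For the residual RR, take a = s and c = 1 − s in the proxy-positive stratum, and the reverse in the proxy-negative stratum. In each group the stratum share is q = p·a + (1 − p)·c and the relative risk is r = 1 + (R − 1)·p·a/q. The Mantel-Haenszel weight is w = qE·qC/(qE + qC), and residual RR = Σ w·rE / Σ w·rC.

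Low end (pE = 0.55, pC = 0.50, R = 2, s = 0.90):
- Proxy-positive shares 0.54 and 0.50, risks 1.917 and 1.900, w = 0.2596.
- Proxy-negative shares 0.46 and 0.50, risks 1.120 and 1.100, w = 0.2396.
- Residual RR = 0.7658/0.7568 = 1.012.

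High end (pE = 0.65, pC = 0.50, R = 3, s = 0.70):
- Proxy-positive shares 0.56 and 0.50, risks 2.625 and 2.400, w = 0.2642.
- Proxy-negative shares 0.44 and 0.50, risks 1.886 and 1.600, w = 0.2340.
- Residual RR = 1.1349/1.0084 = 1.125.

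All cases, with values for R = 2 and R = 3:

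| pE / pC | Crude | Residual, s = 0.70 | Residual, s = 0.90 |
|---|---|---|---|
| 0.50 / 0.50 | 1.000, 1.000 | 1.000, 1.000 | 1.000, 1.000 |
| 0.55 / 0.50 | 1.033, 1.050 | 1.028, 1.042 | 1.012, 1.018 |
| 0.60 / 0.50 | 1.067, 1.100 | 1.056, 1.084 | 1.024, 1.035 |
| 0.65 / 0.50 | 1.100, 1.150 | 1.084, 1.125 | 1.036, 1.053 |
| 0.50 / 0.55 | 0.968, 0.952 | 0.973, 0.960 | 0.988, 0.983 |
| 0.50 / 0.60 | 0.938, 0.909 | 0.947, 0.923 | 0.977, 0.966 |
| 0.50 / 0.65 | 0.909, 0.870 | 0.923, 0.889 | 0.965, 0.950 |

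In the first four rows 50% is the non-users' share; in the last three it is the users' share. With the factor itself recorded without error (s = 1) the residual is 1.000 in every row.

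A larger assumed imbalance, 30% in users against 50% in non-users, gives crude 1.3/1.5 = 0.867 and 1.6/2.0 = 0.800. Standardized to the users' proxy distribution, the residuals are 0.886 and 0.826 (s = 0.70) or 0.948 and 0.917 (s = 0.90). The size follows the assumptions. No figure is offered for urgency or for miscounted foot necrosis.

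**The case against.** The strongest reply is that nothing quoted is wrong. The PAD item is a sensible field, Section 6 does not call its list exhaustive, and the notes refer to an Excel sheet that is not shown and may hold more. This stands as a limit: the point concerns the protocol's list and is conditional on abstraction following it.

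A reader might infer that no later analysis could ever recover these variables. That is too strong. The study is retrospective, and charts can be reopened wherever they document the items. The fair statement is that the listed fields alone would not suffice.

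A reader might also infer that the limb results will be biased, or biased for or against the drug. The protocol gives nothing on how severity or urgency is distributed between the groups, and they may be balanced.

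The proxies deserve credit. The named intervention may separate some acute from chronic cases, and the symptom-progression date set against the procedure date gives a duration. Several proxies together could leave less than the single binary one illustrated. They remain indirect, and some may be absent for the patients in question.

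On foot necrosis, asking for occurrence after the procedure naturally means new events, and excluding planned partial amputation removes some patients with tissue loss. It does not follow that old necrosis will be counted as new, only that the listed fields offer no way to check. This is a secondary ascertainment matter and should not carry the weight of the point.

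**Conclusion.** The point holds in conditional form. The protocol admits a wide range of limb presentations into a non-randomized comparison and lists no direct baseline measure of urgency, acute versus chronic presentation, ischemia stage or tissue loss. If exactly these fields are abstracted, adjustment of the MALE and amputation contrasts would be incomplete wherever the groups differ on these factors.

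Size and direction cannot be derived from the document. The illustrated residuals, including exactly 1.00 when there is no imbalance, show the mechanism and are not estimates; in the milder cases they are only about 1 to 4%. This is a change that should be made, with medium confidence because the data sheet is unseen. It is not a demonstrated bias.

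**What to change.** Before abstraction is completed, add to Section 6, from admission and operative notes, with NZ where the information is unavailable:

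1. acute or chronic ischemia;
2. elective or urgent procedure;
3. limb ischemia stage on a single pre-specified scale (for example the Rutherford classification, in its acute or chronic version as applicable);
4. foot ulcer at admission, yes or no;
5. foot necrosis at admission, yes or no, with site and extent.

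Use these as adjustment or propensity covariates for the limb outcomes.

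Count Section 7 item j as an outcome only if necrosis was absent at admission or has extended beyond the recorded baseline. Where the baseline is NZ, report the event as undetermined and run sensitivity analyses that count it once as new and once as pre-existing.

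The cost is somewhat longer abstraction, reopening any charts already abstracted, some judgment in staging from old notes, and some NZ values, mainly for stage and extent. If the Excel sheet already holds these fields, listing them in Section 6 and adding the counting rule is enough.
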